#### 4.0 Test Schedule

Tests and procedures	Baseline (<21 days prior to registration)	Radiation Treatment Planning	During Radiation Treatment	End of Radiation Treatment +/- 3 days	1 month post RT +/- 7 days	3 months post RT +/- 14 days	At every clinically indicated follow-up 
Physical examination, weight, ECOG PS	X			X	X	X	X
Neurologic history and examination	X 			X	X	X	X
Document current medications	X			X	X	X	X
Pregnancy test	X 						
QOL Assessment: MDASI-BT and BFI 	X 			X	X	X	X 
Standard Mayo glioma brain MRI with and without contrast		X 			X	X	X 
 F-DOPA-PET		X 3,R					
 F-DOPA adverse event assessment		X 					
CT simulation for radiotherapy planning		X 					
Adverse event assessment 	X		X 	X	X	X	X

1. For women of childbearing potential only. Must be done  $\leq 48$  hours prior to injection of study drug. Note: For a positive pregnancy test prior to the pre-RT  $^{18}\text{F}$ -DOPA injection the patient will not undergo the  $^{18}\text{F}$ -DOPA PET scan and will instead be taken off study with no follow-up.
2.  $^{18}\text{F}$ -DOPA post-injection AE assessment: done approximately 40-45 minutes post injection of  $^{18}\text{F}$ -DOPA by the Nuclear Medicine technologist performing the study. If an AE was observed, a second AE assessment is required  $\leq 24$  hours post injection. This assessment will be completed by the study staff. This information will be used for MCCC DSMB review (Section 16.91) and reporting of any AEs under  $^{18}\text{F}$ -DOPA IND (Section 10.0).
3. Must be completed  $\leq 14$  days prior to the start of radiotherapy.
4. CT simulation can be performed prior to or after registration.
5. All follow-up serial imaging after initial treatment will occur until progression or up to 2 years. Typical timing of scans is every 2-3 months or until progression. However, the actual timing of scans for protocol patients will be per the clinician's discretion.
6. To be assessed by Radiation Oncologist at baseline and during radiotherapy and Medical Oncologist for follow-up assessments for MCCC DSMB review (Section 16.91). Adverse events will be assessed weekly during routinely scheduled management visits (+/- 3 days)
7. Maximum grade of adverse events experienced during radiotherapy can be recorded at the end of treatment.
8. Follow up assessments will be completed as per clinician's discretion
9. Neurologic history and examination will be completed by treating Radiation Oncologist
10. Quality of Life (QOL) and cognitive function will be evaluated with MD Anderson Symptom Inventory Brain Tumor Module (MDASI-BT) and the Brief Fatigue Index (BFI).
11. Patient will be asked to complete questionnaires at baseline and at each MRI evaluation for a maximum of 6 evaluations.

R. Research funded

**5.0 Grouping/Stratification Factors:**  
None

## **6.0 Registration Procedures:**

Patient will be registered to the study when they have consented, met eligibility criteria and have been logged into the Research Participant Tracking system (Ptrax).

- 6.1 Verify following procedures are complete prior to Registration to the study.
  - 6.11 Prior to accepting the registration, verify the following:
    - 6.12 IRB approval at the registering institution
    - 6.13 Patient eligibility complete
    - 6.14 Existence of a signed informed consent
    - 6.15 Existence of a signed authorization for use and disclosure of protected health information (optional)
- 6.2 Radiation therapy on this protocol must be performed at Mayo Clinic Rochester under the supervision of a radiation oncologist.
- 6.3 Tests and procedures (Section 4.0) must be completed within the guidelines specified on the test schedule.

## 7.0 Protocol Treatment

### 7.1 CT simulation

The patient will be immobilized with a BrainLab mask and a CT dataset acquired of the patient for treatment planning as per standard of care during the CT simulation appointment.

### 7.2 F-DOPA-PET

#### 7.21 Timing of PET scanning:

The PET scan to be used for radiation treatment planning should be acquired no more than 14 days prior to beginning radiation treatments.

#### 7.22 Patient preparation for PET scan

7.221 A negative pregnancy test must be done  $\leq 48$  hours prior to F-DOPA injection for women of child-bearing potential only.

7.222 Patients will be instructed to follow a low-protein diet after the previous evening meal. Liberal hydration 24 hours before the exam will be encouraged. Carbidopa, used for Parkinson's patients to inhibit decarboxylation of the F-DOPA tracer, is not necessary for brain tumor imaging.

#### 7.23 Selection of patients for PET/CT or PET/MRI

7.231 PET/MRI is the planned method for obtaining anatomic correlation with F-DOPA PET. PET/CT information is provided below in the circumstance that F-DOPA/MRI is not possible/available. All requests to utilize F-DOPA PET/CT will require approval from nuclear medicine and radiation oncology study chairs.

#### 7.24 PET/CT

7.241 A total of 5.0 + 10% mCi of F-DOPA will be intravenously injected. A scout image will be acquired in order to prescribe the scan range for the image acquisition. CT images will be obtained and used for attenuation correction of the PET data and, at 10 minutes after injection of F-DOPA, a 20 minute 3D PET acquisition will be acquired. The PET data will also be acquired concurrently in list mode; this data will be used to salvage a scan should the patient move. The PET sinograms will be reconstructed with a fully 3D-OSEM algorithm into a 300 mm field of view with a pixel size of 1.17mm and slice thickness of 1.96mm. All images will be transferred to a Radiation Oncology workstation.

#### 7.25 PET/MRI

- 7.251 The subject will undergo MRI screening for contraindications to scanning and contrast agent administration as per routine clinical protocol at Mayo Clinic. MRI will be acquired on a PET/MR scanner simultaneously during the 20 minute PET acquisition phase.
- 7.252 A total of 5.0 + 10% mCi of F-DOPA will be intravenously injected. A scout image will be acquired in order to prescribe the scan range for the image acquisition. MR images will be obtained and used for attenuation correction of the PET data and, at 10 minutes after injection of F-DOPA, a 20 minute 3D PET acquisition will be acquired. The PET data will also be acquired concurrently in list mode; this data will be used to salvage a scan should the patient move. The PET sinograms will be reconstructed with a time-of-flight algorithm into a 300 mm field of view with a pixel size of 1.17mm and slice thickness of 2.78mm. All images will be transferred to a Radiation Oncology workstation.
- 7.253 The following MRI sequences will be obtained: Sagittal T1 FLAIR, Axial DWI, Axial T2 FLAIR, Axial BRAVO ARC, Gad Axial T2, Gad Sagittal Cube T1.

### 7.3 MRI Scanning

#### 7.31 Patients requiring a separate diagnostic MRI

Patients undergoing PET/CT will require a separate diagnostic MRI. Patients undergoing PET/MRI may omit this step, as diagnostic-quality images will be obtained with PET/MRI.

#### 7.32 Screening for MR eligibility

The subject will undergo MRI screening for contraindications to scanning and contrast agent administration as per routine clinical protocol at Mayo Clinic.

#### 7.33 Timing of MR scanning

MRI will be acquired at the time of the standard CE-MRI examination on a 3.0 Tesla field strength scanner, no more than 14 days prior to beginning radiation treatments

Note: Standard treatment planning protocols will be used at the discretion of the radiation oncologist and radiologist, including T1-post contrast and T2 FLAIR sequences at a minimum

7.4 Comparison of volumes

To examine volumes delineated using F-DOPA-PET and MRI, the union, intersection and discordant regions of PET and MR volumes will be quantified. For patients with PET uptake outside of the MR volume, the percentage of PET uptake encompassed by several different margins beyond the MR defined volume will be determined, and the maximal distance (in millimeters) between the margin of the MR volume and the margin encompassing 100% of the PET uptake will be quantified. Both PET T/N ratio >2.0 and T/N ratio > 1.5 will be used to define the PET volume.

7.41 Exploratory analysis for other T/N thresholds and SUV levels will be investigated

7.5 Radiation therapy

7.51 Target delineation

Following informed consent and co-registration of PET and MRI datasets with the planning CT acquired during standard CT simulation, the radiation oncologist will define the target volumes to use for radiation treatment planning.

7.52 Target delineation will be based on MRI and PET imaging, defining a gross tumor volume (GTV), clinical target volume (CTV), and planning target volume (PTV) as defined below. In the event that gross disease is multifocal on MRI or FDOPA-PET, contours do not need to be contiguous.

- 7.5121 GTV\_MRI = standard of care MRI contrast enhancement
- 7.5122 GTV\_PET = high signal PET disease
- 7.5123 GTV\_high = boolean of GTV\_MRI and GTV\_PET
- 7.5124 CTV\_high = GTV\_high
- 7.5125 PTV\_high = CTV\_high with a 0-2 mm expansion, based on the radiation oncologist’s clinical judgment

7.53 Treatment planning and delivery

The prescription dose will be 35 Gy delivered in 10 fractions of 3.5 Gy each. Treatments will be delivered daily except weekends and holidays.

7.531 For PTV\_high volumes less than 75 cc, a dose of 40 Gy in 10 fractions is allowed

7.532 Target coverage and normal tissue constraints are outlined below

Structure	Constraints Goals			Highest Priority Constraints		
	DVH Endpoint	Constraint	Priority	DVH Endpoint	Constraint	Priority

CTV_high	D95%[%]	>=100%	2	D95%[%]	>=95%	1
	-	-	-	CV95%[cc]	<0.5cc	1
	V110%		Report	-	-	-
PTV_high	D95%[%]	>=99%	2	D95%[%]	>=95%	1
	-	-	-	CV95%[cc]	<0.5 cc	1
	V110%		Report	-	-	-
Brain-ptv	-	-	-	V36Gy	<0.1 cc	1
	V31Gy[cc]	<1 cc	2	-	-	-
	V28Gy[cc]	<5 cc	2	-	-	-
	-	-	-	D0.03cc	<35 Gy	1
Optic_chiasm_PRV	D0.03cc	<20 Gy	2	D0.03cc	<25 Gy	1
Optic_chiasm	-	-	-	Dmax	-	Report
Optic_nerve_l_PRV	D0.03cc	<20 Gy	2	D0.03cc	<25 Gy	1
Optic_nerve_l	-	-	-	Dmax	-	Report
Optic_nerve_r_PRV	D0.03cc	<20 Gy	2	D0.03cc	<25 Gy	1
Optic_nerve_r	-	-	-	Dmax	-	Report
Brainstem	D0.03cc	<24 Gy	2	D0.03cc	<30 Gy	1
Cord	-	-	-	Dmax	-	Report
Lens_r	D0.03cc	<4 Gy	2	-	-	-
Lens_l	D0.03cc	<4 Gy	2	-	-	-
Eye_r	Mean	≤20 Gy	2	-	-	-
	D0.03cc	<35 Gy	2	-	-	-
Eye_l	Mean	≤20 Gy	2	-	-	-
	D0.03cc	<35 Gy	2	-	-	-
Parotid_r	Mean	<16 Gy	2	-	-	-
Parotid_l	Mean	<16 Gy	2	-	-	-
Cochlea_r	D0.03cc	<35 Gy	2	-	-	-
	Mean	<20 Gy	2	-	-	-
Cochlea_l	D0.03cc	<35 Gy	2	-	-	-
	Mean	<20 Gy	2	-	-	-
Hippocampus_l	Mean	≤20 Gy	2	-	-	-
Hippocampus_r	Mean	≤20 Gy	2	-	-	-

- 7.54 Brain constraints were determined using the cumulative normal tissue dose( $NTD_{cumulative}$ ) constraint of 100 Gy in 2 Gy fractions (assuming  $\alpha/\beta=2$  for late brain toxicity) reported by Mayer et al. to minimize the risk of radiation necrosis.[30] Assuming the brain received a previous dose of 60 Gy in 30 fractions, keeping the dose less than or equal to 31 Gy will result in an  $NTD_{cumulative}$  of 99.5 Gy.
- 7.55 If the patient previously received less than 60 Gy in 2 Gy equivalent fractions, the brain constraint can be relaxed as to keep the  $NTD_{cumulative}$  below 100 Gy.
- 7.56 Plans created using proton therapy will utilize robust optimization as per the departmental standard. No PTV will be needed for these patients.

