7.57 ExacTrac or PAIS will be used for image guidance

7.58 Plan deviations

	Deviation	
	Minor	Major
Target volumes	CTV_high D95% between 90% and 95%	CTV_high D95% <90%
Volume	CTV or PTV margins larger than allowed in the protocol	Contoured GTV does not include imaging-visible tumor
Organs at Risk	Will be assessed at the time of data review	Will be assessed at the time of data review

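### At 40 Gy, highest-priority PTV coverage and the fixed Brain-ptv limits are not realistically compatible for photon plans bordered mostly by brain after about 60 Gy prior dose

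*Combined protocol and SAP*

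**What the plan says.** Section 7.53 sets the base prescription: "The prescription dose will be 35 Gy delivered in 10 fractions of 3.5 Gy each". Section 7.531 adds an option: for PTV_high "volumes less than 75 cc, a dose of 40 Gy in 10 fractions is allowed".

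The constraint table in 7.532 serves both prescriptions.

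- **Target rows are relative to prescription.** The PTV coverage row reads "PTV_high D95%[%] >=99% 2 D95%[%] >=95% 1", so 95% of prescription to 95% of the PTV is priority 1. The CTV_high block also carries "CV95%[cc] <0.5cc 1", and PTV_high has the same limit at the same priority.
- **Brain-ptv rows are in absolute Gy.** Priority 1 is "V36Gy <0.1 cc 1". A further priority-1 row, "D0.03cc <35 Gy 1", follows under Brain-ptv in the extracted table without a structure label of its own. The 31 Gy and 28 Gy rows are priority 2.

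Section 7.54 derives the brain constraints from a cumulative normal tissue dose of 100 Gy in 2 Gy fractions, with α/β = 2, and states that 31 Gy after 60 Gy in 30 fractions gives 99.5 Gy. Section 7.55 allows the brain limit to be relaxed when the earlier dose was below 60 Gy, provided the cumulative figure stays under 100 Gy. Section 7.56 says of proton plans: "No PTV will be needed for these patients". Section 3.21 excludes prior doses above 60 Gy to the target, so patients with exactly 60 Gy are eligible.

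**The concern.** PTV_high and Brain-ptv share a border. When the prescription rises from 35 to 40 Gy, the dose required on the target side of that border rises with it, and the dose permitted on the brain side does not. Both rows are priority 1, and the protocol does not say which gives way.

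The planner of such a 40 Gy plan must then choose between losing coverage and exceeding a brain limit meant to control necrosis in irradiated tissue. Different planners may choose differently. The dose actually delivered would vary in a 20-patient study whose endpoints include progression at 3 months and late toxicity.

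Two further problems sit in the same sections. The priority-1 brain levels do not follow from the cumulative-dose rule said to generate them. For proton plans, the volume gate and the brain structure refer to a PTV that need not exist.

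**Working it through.** **1. Reproduce the plan's own figure (7.54).** With n = 10 fractions and α/β = 2, EQD2 = D × (D/10 + 2) / (2 + 2).

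31 × (3.1 + 2) / 4 = 39.525; plus 60 = 99.525 Gy. This matches the stated 99.5 Gy.

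**2. Apply the same formula to the other levels, after 60 Gy in 30 fractions.**

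| Level (10 fractions) | EQD2 | Cumulative | Prior EQD2 below which the total stays under 100 Gy |
|---|---|---|---|
| 31 Gy (priority 2) | 39.5 | 99.5 | 60.5 |
| 35 Gy (priority 1) | 48.1 | 108.1 | 51.9 |
| 36 Gy (priority 1) | 50.4 | 110.4 | 49.6 |
| 38 Gy (coverage floor at 40 Gy) | 55.1 | 115.1 | 44.9 |

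Only the 31 Gy level agrees with 7.54. The last column gives the reach of 7.55: the brain limit rises to 38 Gy only if prior EQD2 is below about 44.9 Gy. A prior 54 Gy allows 34.05 Gy, and a prior 50 Gy allows 35.8 Gy.

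**3. Convert coverage to Gy.** 0.95 × 35 = 33.25 Gy, below both 35 and 36 Gy, so there is no conflict. 0.95 × 40 = 38 Gy, which is 2 Gy above the V36Gy level and 3 Gy above the D0.03cc level.

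**4. Find the distance available for the fall from 38 to 36 Gy.** Assume a spherical PTV wholly surrounded by brain, and read CV95% (undefined in the text) as the volume receiving less than 95%. The cold volume allowed inside the surface plus the 0.1 cc allowed outside, divided by the surface area, gives the thickness. The needed gradient is 2 Gy divided by that thickness.

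| PTV | Area | Both coverage rows: (0.5 + 0.1) cc / area | Gradient | D95% row only: (5% of PTV + 0.1 cc) / area | Gradient |
|---|---|---|---|---|---|
| 20 cc | 35.6 cm² | 0.17 mm | 11.9 Gy/mm | 0.31 mm | 6.5 Gy/mm |
| 50 cc | 65.6 cm² | 0.09 mm | 21.9 Gy/mm | 0.40 mm | 5.0 Gy/mm |
| 75 cc | 86.0 cm² | 0.07 mm | 28.7 Gy/mm | 0.45 mm | 4.5 Gy/mm |

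If the D0.03cc row does belong to Brain-ptv, 3 Gy must fall within (0.5 + 0.03) cc / area: 0.15, 0.08 and 0.06 mm, or about 20, 37 and 49 Gy/mm.

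**5. Range over assumed gradients.** The documents give none; I take 2, 4 and 10 Gy/mm (5%, 10% and 25% of 40 Gy per mm). Place the 36 Gy surface as far out as V36Gy allows. The PTV volume below 38 Gy is then 3.3, 1.6 and 0.6 cc for a 20 cc PTV, and 8.2, 4.1 and 1.6 cc for 75 cc. The limit is 0.5 cc. Coverage at 38 Gy is 84%, 92% and 97% at 20 cc, and 89%, 94.5% and 98% at 75 cc. D95% therefore fails at 2 and 4 Gy/mm. At 10 Gy/mm D95% is met and only the cold-volume row fails. A 10 cc PTV would pass both rows at 10 Gy/mm (0.35 cc cold) when V36Gy is the only brain limit.

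**6. Brain on part of the border.** The thickness scales with 1/(fraction of surface facing brain). At one tenth, using both coverage rows and V36Gy, the needed gradient falls to 0.7 Gy/mm at 10 cc and 2.9 Gy/mm at 75 cc.

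**7. Protons.** If the CTV stood in for the missing PTV at the gate, a 75 cc sphere (radius 2.616 cm) less a 2 mm margin is 59.1 cc. CTVs of about 59 to 75 cc would then qualify with protons but not with a full 2 mm photon margin. At the permitted 0 mm margin the difference vanishes.

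**The case against.** A reader might infer that every 40 Gy plan must break a priority-1 row. The documents do not support that. The two limits apply to volumes that do not overlap, so 38 Gy in one and under 36 Gy in the other is not a numerical contradiction. A PTV with little brain on its border could comply, and so could a small PTV under a very steep gradient. Section 7.55 relaxes the limit for lower prior doses, and 3.21 sets no minimum prior dose. A proton plan with no PTV has no Brain-ptv row to break.

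A reader might also infer that the protocol forces a breach. It does not: 40 Gy is permitted, not required, and the rows fit together at 35 Gy.

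Nor does 7.58 let brain excess pass unseen. Besides CTV coverage, it scores oversized margins and a GTV that omits visible tumour. For organs at risk it says "Will be assessed at the time of data review". CNS necrosis is a listed radiation event in 10.10, and irreversible grade 3 or 4 CNS toxicity counts toward the suspension rule in 16.91.

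The unlabelled D0.03cc row deserves caution. If it belongs to Brain-ptv it makes V36Gy redundant, since less than 0.03 cc at 35 Gy already means less than 0.1 cc at 36 Gy. A label may have been lost when the table was read.

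All of this limits the point without removing it. Patients with 60 Gy prior are eligible and 60 Gy is the protocol's own planning assumption; they gain nothing from 7.55. The V36Gy row alone produces the conflict.

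**Conclusion.** The point holds in a bounded form. For photon plans at 40 Gy, after a prior dose near 60 Gy and with brain around most of the PTV, the priority-1 coverage and brain rows are not realistically achievable together. The 2 Gy fall must fit within 0.07 to 0.45 mm for PTVs of 20 to 75 cc. This rests on a spherical PTV, on a reading of CV95% for the smaller figures, and on the judgement that gradients of 4.5 to 29 Gy/mm are not to be expected around the whole surface. The documents supply no gradient, so that judgement is an assumption.

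Two parts need no gradient. The 35 and 36 Gy levels imply cumulative doses of 108.1 and 110.4 Gy against the stated 100 Gy, after 60 Gy prior. The 75 cc gate and Brain-ptv rely on a structure that 7.56 does not require for proton plans.

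Because the limits concern necrosis risk and the correction is wording only, the passages should be reconciled.

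**What to change.** The sponsor should reconcile 7.531, 7.532 and 7.54 to 7.56 so that they state:

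- which brain limits apply at each prescription, and the NTD_cumulative that each implies under the assumptions of 7.54;
- which structure the D0.03cc row belongs to, and what CV95% means;
- which priority-1 row yields when both cannot be met;
- which structure defines the 75 cc gate and the brain-minus-target volume for proton plans.

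A brain threshold in the 7.58 deviation table would be a useful but optional addition. No dose or limit is proposed here; those values are for the sponsor to decide. The cost is a wording amendment, with no extra patients or procedures.

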### 1.2 F-DOPA-PET offers better localization of primary tumor than MRI alone:

While it is well established that regions of contrast enhancement and edema are likely to contain tumor, it is thought that infiltration of tumor may additionally occur along neuronal tracts.[7] Given that up to 20% of patients may experience progression outside the aforementioned MRI changes, a need exists to develop a complementary imaging modality. While standard 18-fluoro-deoxyglucose positron emission tomography (F-FDG-PET) is generally insufficient in visualizing brain tumors, amino acid PET tracers, such as 3,4-dihydroxy-6-[F] fluoro-L-phenylalanine (F-DOPA) offer several advantages.[8] F-DOPA-PET shows high uptake in tumor tissue and low uptake in normal tissue. Unlike contrast enhancement, F-DOPA-PET crosses the intact blood brain barrier freely via an amino acid transporter.[9] In a pilot study at Mayo Clinic, increased F-DOPA-PET uptake was seen in 13 of 16 high-grade biopsy specimens, while MRI T1 contrast enhancement was only present in 6 of the 16 specimens.[10] With this knowledge, Mayo Clinic is currently enrolling patients with newly-diagnosed high-grade gliomas in a radiotherapy trial where dose-escalation is planned for regions of high F-DOPA uptake.

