#### 1.6 Reirradiation is often used for treatment of progression:

Repeat courses of radiotherapy are often considered for progressive disease refractory to systemic therapy. Conventionally fractionated doses between 36 and 46 Gy have been used with minimal neurologic toxicity.[21-23] Hypofractionated doses of 24-50 Gy in 3.5-5 Gy fractions have also been used with minimal toxicity when limiting doses to <40 Gy.[22, 24-29] Mayer and colleagues proposed a cumulative normal tissue dose limit (2 Gy per fraction equivalent) of <100 Gy to limit the risk of radionecrosis.[30] In general, the target volume includes a minimal expansion beyond MRI contrast enhancement.[21, 24-27, 29] Median survival after reirradiation ranges from 7 to 10 months.[21-27, 29] The best outcomes are seen when more time elapses between primary radiation and reirradiation and in patients with lower-grade histology.[24-26, 31] In an analysis of patterns of recurrence after reirradiation, 60-70% recurrences were located in-field with the remainder located out of field.[25, 32] Thus, MRI contrast enhancement may not accurately reflect tumor location potentially resulting in imprecise targeting of radiation target volumes.

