#### 3.2 Exclusion Criteria

- 3.21 More than one prior course of radiotherapy or prior prescription doses exceeding 60 Gy to re-irradiation target volumes
- 3.22 Unable to undergo MRI scans with contrast
- 3.23 Unable to undergo an  $^{18}\text{F}$ -DOPA-PET scan (e.g., Parkinson's Disease, taking anti dopaminergic, or dopamine agonist medication or less than 6 half-lives from discontinuance of dopamine agonists.)

Note: Other potentially interfering drugs: amoxapine, amphetamine, benztropine, bupropion, buspirone, cocaine, mazindol, methamphetamine, methylphenidate, norephedrine, phentermine, phenylpropanolamine, selegiline, paroxetine, citalopram, and sertraline). If a patient is on any of these drugs, list which ones on the On-Study form.

- 3.24 Any of the following:
  - Pregnant women
  - Nursing women
  - Men or women of childbearing potential who are unwilling to employ adequate contraception

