Using the radiation treatment dosing, fractionation and normal tissue constraints outlined in Section 7 have been performed in several studies without significant adverse effects. While radiation-induced brain necrosis is rare, a cumulative normal brain dose of < 100 Gy in 2 Gy equivalents has been suggested as a constraint to minimize the risk of necrosis.[30] Two large studies reported no grade 3 or higher toxicity and no radionecrosis using the same dosing and fractionation as our protocol.[26, 27] In fact, studies using larger fraction sizes (5 Gy/fraction) reported very low rates of radionecrosis when keeping reirradiation doses under 40 Gy.[28, 29] However, tumor progression is expected in the majority of patients and commonly results in severe neurologic symptoms near the end of life. Both acute (available at <http://ctep.cancer.gov>) and late [39] toxicity will be monitored continuously as each patient is accrued and follow-up data are accumulated. If at any time, 1) 3 or more of the first 9 AE-evaluable patients; or, 2) after 10 or more patients are AE-evaluable, more than 30% experience any of the following adverse effects considered to be at least possibly related to radiation treatment up to and including the three-month timepoint; enrollment will be suspended so the details of each episode may be examined and a trial recommendation will be formulated and presented to the MCCC DSMB, adjusting the dose, fraction size or volumes as needed.

- Grade 3 or 4 irreversible CNS toxicity
- Grade 4 non-hematologic, non-CNS toxicity
- Any Grade 5 toxicity

Initial estimated Primary Completion Date: At study activation, this study will have been registered within the www.ClinicTrials.gov (CT.gov) website. The Primary and Secondary endpoints along with other required information for this study will be reported on CT.gov. For purposes of timing of the CT.gov results reporting, the initial estimated completion date of the primary endpoint of this study is 27 months after the study opens to accrual.

16.101 Definition of Primary-Endpoint Completion Date (PCD): The PCD is the date at which the last progression free patient has been followed for 3 months.

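### Section 7.55 adjusts the brain planning goals for lower prior doses only; above about 60.5 Gy equivalent in adjacent brain, the volume they allow over 100 Gy loosens from under 1 cc to under 5 cc (minor)

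*Combined protocol and SAP*

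**What the plan says.** All references are to the combined protocol and SAP.

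- Section 1.6 reports, from the reirradiation literature, "a cumulative normal tissue dose limit (2 Gy per fraction equivalent) of <100 Gy to limit the risk of radionecrosis". Section 16.91 repeats the figure: "a cumulative normal brain dose of < 100 Gy in 2 Gy equivalents has been suggested as a constraint".
- Section 7.54 turns it into a planning dose with alpha/beta = 2: "Assuming the brain received a previous dose of 60 Gy in 30 fractions, keeping the dose less than or equal to 31 Gy" gives a cumulative 99.5 Gy.
- The table under 7.532 carries this as two priority 2 goals for brain outside the PTV: V31Gy <1 cc and V28Gy <5 cc. The priority 1 brain limits are V36Gy <0.1 cc and D0.03cc <35 Gy.
- Section 7.55 adapts the goal to the patient: "If the patient previously received less than 60 Gy in 2 Gy equivalent fractions, the brain constraint can be relaxed", provided the cumulative dose stays below 100 Gy. It has no counterpart for a higher prior dose.
- Exclusion 3.21 bars more than one prior course, or "prior prescription doses exceeding 60 Gy to re-irradiation target volumes".
- Section 1.2 says the same institution is enrolling newly diagnosed patients in a "radiotherapy trial where dose-escalation is planned for regions of high" tracer uptake.

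**The concern.** The 31 Gy level is derived for one reference patient and leaves a margin of less than 0.5 Gy below 100 Gy. Section 7.55 then lets the level move up for patients with more remaining tolerance, but does not ask for it to move down for those with less.

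Exclusion 3.21 limits how often this can arise but does not rule it out. It counts nominal prescribed Gy, so 60 Gy given in fractions larger than 2 Gy is eligible although its 2-Gy equivalent is above 60. It also applies to the re-irradiation target, so brain beside the target may lie in a region that was prescribed more than 60 Gy. For either patient, a plan that meets every written goal can put more brain above the protocol's own cumulative aim than it would for the reference patient.

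What is at stake is the volume of normal brain exposed to the dose range that the protocol links to radionecrosis. The primary endpoint, sample size and error rates are not affected.

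**Working it through.** **Inputs.** Cumulative aim 100 Gy, alpha/beta = 2 and reference prior 60 Gy in 30 fractions (7.54); 10 re-irradiation fractions (7.53); brain goals and limits (table under 7.532).

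**Formula.** 2-Gy equivalent = D × (d + 2)/4, where D is total dose and d is dose per fraction.

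**1. The plan's own figure.** 60 Gy in 30: 60 × 4/4 = 60.0. 31 Gy in 10: 31 × 5.1/4 = 39.525. Sum 99.525, which agrees with the stated 99.5 Gy.

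**2. Break-even priors.** 31 Gy level: 100 − 39.525 = 60.475. 28 Gy level: 28 × 4.8/4 = 33.6, and 100 − 33.6 = 66.4.

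**3. What the unchanged goals then bound.**
- Prior up to 60.475: brain above 100 Gy lies within the volume above 31 Gy, so under 1 cc.
- Prior between 60.475 and 66.4: the re-irradiation dose that brings the total to 100 Gy falls between 28 and 31 Gy. Only V28Gy applies, so under 5 cc.
- Prior above 66.4: neither priority 2 goal bounds it.

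**4. What those priors mean in practice.** With 60 Gy prescribed, the fraction sizes are 60.475 × 4/60 − 2 = 2.03 Gy and 66.4 × 4/60 − 2 = 2.43 Gy. For adjacent brain treated in 30 fractions, solving D(D/30 + 2)/4 = 60.475 and 66.4 gives totals of 60.3 and 64.2 Gy.

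**5. Illustrations.** Apart from 60 Gy in 30, the prior schedules are assumed; the documents give none.

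| Prior | 2-Gy equivalent | Total at 31 Gy | Total at 28 Gy |
|---|---|---|---|
| 60 Gy/30 (reference) | 60.0 | 99.5 | 93.6 |
| 62 Gy/30, adjacent brain | 63.0 | 102.6 | 96.6 |
| 55 Gy/20 | 65.3 | 104.8 | 98.9 |
| 60 Gy/25 | 66.0 | 105.5 | 99.6 |
| 59.4 Gy/33 | 56.4 | 96.0 | 90.0 |
| 50 Gy/20 | 56.3 | 95.8 | 89.9 |
| 40.05 Gy/15 | 46.8 | 86.3 | 80.4 |

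**6. Level that would hold 100 Gy in 10 fractions.** Solve D²/10 + 2D = 4 × (100 − prior), so D = −10 + √(100 + 40 × (100 − prior)). Prior 60.0 gives 31.2 Gy; 63.0 gives 29.7; 65.3 gives 28.6; 66.0 gives 28.2; 66.4 gives 28.0.

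**7. How firm the 100 Gy aim is.** At the reference prior, the priority 1 limit of 35 Gy to 0.03 cc is 35 × 5.5/4 = 48.1 Gy equivalent, a total of 108.1 Gy. The plan therefore already accepts very small volumes above 100 Gy.

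**The case against.** The case for leaving 7.55 alone is substantial.

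- **Eligibility.** Read together, 3.21 and 7.54 suggest that 60 Gy was meant as the ceiling, so only lower priors needed a rule. This fits the likely intent. The wording of 3.21 still leaves out 2-Gy equivalents and adjacent brain.
- **Both routes are assumed.** No hypofractionated prior of 55 to 60 Gy appears in the documents. Section 1.2 gives no escalated dose and does not say that those patients enter this trial. A target overlapping a region prescribed above 60 Gy is already excluded, so that route needs a target beside such a region, with the 28 to 31 Gy shell reaching into it. Only the overlapping part counts, so 5 cc is a ceiling. This stands, and it limits the importance of the point.
- **The aim is soft.** The 100 Gy value is described as proposed or suggested, the goals are priority 2, and they cover only brain outside the PTV. This stands.
- **Other safeguards.** The goals are upper bounds, and a planner may go lower. A radiation oncologist supervises (6.2), bevacizumab is recommended (7.6), CNS necrosis is graded (10.10), and 16.91 has a CNS toxicity suspension rule. These help only in part. That rule counts events up to three months, while 7.54 treats the brain harm as late; 7.58 sets no organ-at-risk deviation threshold in advance.
- **Cost.** Section 7.55 is permissive, so prior dose need be converted only if the team chooses to relax. A tightening rule would make local conversion compulsory for some patients. This stands, although 3.21 already requires locating the prior prescription relative to the new target.

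**Conclusion.** The rule is one-sided and the thresholds reproduce. For an eligible patient whose adjacent brain had more than about 60.5 Gy equivalent, the unchanged priority 2 goals loosen the volume allowed above 100 Gy from under 1 cc to under 5 cc, for priors up to 66.4 Gy equivalent. This rests on the protocol's alpha/beta of 2, delivery in 10 fractions, and the goals being met. It is a minor, optional-level safety improvement.

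A reader might infer more, and the documents do not support it:

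- That 7.55 breaches a hard safety limit. The plan does not hold even its reference patient strictly to 100 Gy.
- That heavily pre-treated patients will be enrolled, or that excess necrosis should be expected. No prior schedules, escalated doses or frequencies are given; among at most 22 patients the number affected may be zero.
- That making the rule symmetric would secure 100 Gy. It would restore the intended soft volume bound, no more.

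**What to change.** Add one sentence to 7.55, for example: *When the prior dose to brain adjacent to the new target exceeded 60 Gy in 2-Gy equivalents (alpha/beta = 2), the priority 2 brain goals are lowered so that the cumulative dose stays below 100 Gy where achievable; priority 1 target coverage and brain limits are unchanged.* The values in step 6 of the working could serve as a guide: the 31 Gy level becomes about 29.7 Gy for a prior of 63.0 and 28.2 Gy for 66.0. The clinical team should set the final values. Exclusion 3.21 can stay as it is.

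There are two costs. For each patient with a high or hypofractionated prior, the dose near the new target must be obtained and converted to 2-Gy equivalents. This includes patients first treated elsewhere, since 3.14 does not require prior treatment at this institution. A few plans may also lose some target-edge coverage at the priority 2 level (CTV D95% ≥100%, PTV D95% ≥99%); the priority 1 minimum of 95% still takes precedence. No visit or eligibility change is needed.
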